11.1 Monitoring

11.1.1 External Data Monitoring Committee

No data monitoring committee is planned for this study.

11.1.2 Monitoring of the Study

The clinical monitor, as a representative of the sponsor, has the obligation to follow the study

closely.	
	8

11.1.3 Inspection of Records

Investigators and institutions involved in the study will permit study-related monitoring, audits, IRB/IEC review, and regulatory inspections by providing direct access to all study records.

11.2 Management of Protocol Amendments and Deviations

11.2.1 Modification of the Protocol

Any changes in this research activity, except those necessary to remove an apparent, immediate hazard to the patient, must be reviewed and approved by the sponsor or its designee. Amendments to the protocol must be submitted in writing to the investigator's IRB/IEC for approval before patients can be enrolled into an amended protocol.

11.2.2 Protocol Deviations

The investigator or designee must document and explain in the patient's source documentation any deviation from the approved protocol.

11.3 Study Termination

Although Aeon Biopharma, Inc. has every intention of completing the study, Aeon Biopharma, Inc. reserves the right to discontinue the study at any time for clinical or administrative reasons.

The end of the study is defined as the date on which the last patient completes the EOS visit (ie, 52 weeks after Day 0 "rollover"), patient withdrawal (for any reason), or study discontinuation by the sponsor.

11.4 Final Report

Whether the study is completed or prematurely terminated, the sponsor will ensure that the clinical study reports (CSRs) are prepared and provided to the regulatory agencies as required by the applicable regulatory requirements. The sponsor will also ensure that the CSRs in marketing applications meet the standards of the ICH guideline E3: Structure and Content of Clinical Study Reports.

Where required by applicable regulatory requirements, an investigator signatory will be identified for the approval of the CSR. The investigator will be provided reasonable access to statistical tables, figures, and relevant reports and will have the opportunity to review the complete study results.

Upon completion of the CSR, the sponsor will provide the investigator with the full summary of the study results. The investigator is encouraged to share the summary results with the study patients, as appropriate. The study results will be posted on publicly available clinical trial registers.

12 References

ABP-450 13 May 2021

13 Appendices

ABP-450 13 May 2021

ABP-450 13 May 2021

Page 68

ABP-450 13 May 2021

13.2 TWSTRS Scale

ABP-450 13 May 2021

13.4 PGI-C Scale

Aeon Biopharma, Inc. Protocol: ABP-19002 (Version 2.1)

ABP-450 13 May 2021

13.6 Dysphagia Severity Scale

ABP-450 13 May 2021

13.7 C-SSRS Scale

 9. EFFICACY ANALYSIS	17 17 18 and Pain) Scores. 19 20 20 20 20 20 20 20 20 20 21 22 SIS 22 23
 9. EFFICACY ANALYSIS	17 17 18 and Pain) Scores. 19 20 20 20 20 20 20 20 20 20 21 22 SIS 22 23

List of Abbreviations

AE	adverse event
ATC	Anatomical Therapeutic Chemical
BMI	Body mass index
CGI-C	Clinical Global Impression of Change
C-SSRS	Columbia-Suicide Severity Rating Scale
CI	Confidence interval
COVID-19	Coronavirus Disease 2019
CRF	case report form
DSMB	data safety monitoring board
ECG	electrocardiogram
eCRF	Electronic case report form
EOS	End of study
FAS	full analysis set
FEV1	forced expiratory volume in 1 second
FVC	forced vital capacity
HEENT	head, ears, eyes, nose, throat
ICH	International Conference on Harmonisation
ITT	intent-to-treat
MedDRA	Medical Dictionary for Regulatory Activities
mFAS	Modified full analysis set
MITT	modified intent-to-treat
OLE	Open label extension
PGI-C	Patient Global Impression of Change
PPS PT PVG SAF SAF SAF SAF SAF SAF SAF SAF SOC SOP TEAE TWSTRS WHO WHODRUG	per protocol set preferred term Pharmacovigilance Safety analysis set Safety analysis set with retreatment Statistical analysis plan serious adverse event Standard error system organ class Standard operating procedures treatment-emergent adverse events Toronto Western Spasmodic Torticollis Rating Scale World Health Organization World Health Organization drug dictionary

1. Introduction

Cervical dystonia (spasmodic torticollis) is the most common form of focal dystonia, affecting the neck and shoulder muscles (Defazio 2004, Mittal 2019). Cervical dystonia is characterized by abnormal head and neck posture with involuntary head and neck movements. It is often associated with neck and shoulder pain.

Botulinum toxin A is considered first-line therapy for cervical dystonia, helping to improve pain, posture, and disability (Comella 2011, Simpson 2016, Mittal 2019). ABP-450 (prabotulinumtoxinA) is a toxin produced by *Clostridium botulinum*. It blocks neuromuscular transmission by binding to acceptor sites on motor nerve terminals, entering the nerve terminals, and inhibiting the release of acetylcholine. Blocking the release of acetylcholine plays a role in relaxing muscles by reducing muscle activity.

ABP-450 was evaluated in multiple non-clinical safety and toxicological tests to determine the pharmacologic and safety profile of the product to in complying with International Council for Harmonisation of Technical Requirements for Pharmaceuticals for Human Use (ICH) guidelines/requirements for biologic products.

Surdennes, requirements for orongie products.	

PrabotulinumtoxinA has also been found to be non-inferior to BOTOX® for the treatment of moderate to severe glabellar lines in adult patients and upper limb spasticity in patients with stroke

(Nam 2015, Rzany 2019). The doses of ABP-450 used in the Phase 3 study for upper limb spasticity were similar to the doses of BOTOX® used (no significant differences were seen between the 2 groups) (Nam 2015).

ABP-19000 is an ongoing, Phase 2, randomized, double-blind, multicenter, placebo-controlled study to evaluate the safety and effectiveness of intramuscular ABP-450 injection for the treatment of cervical dystonia.

ABP-19002 is the open-label extension (OLE) study, wherein eligible patients from ABP-19000 studies, irrespective of treatment allocation, will have the option to continue treatment with ABP-450.

The ABP-19002 study will help to evaluate safety and efficacy of repeat dosing of ABP-450 for the long-term treatment of cervical dystonia.

Clostridium botulinum toxins have become the standard of care for the treatment of patients with cervical dystonia, but also have significant risks associated with their use in these patients. The labels of marketed products carry prominent warnings concerning their side effects, such as dysphagia and even death, if they are not carefully administered and the patients are not monitored while under treatment. Even so, the benefit for all these products is greater than the potential risk.

Clinical development of drugs has been impacted by the ongoing COVID-19 pandemic. The current study aims to implement several adjustments or mitigations to allow the study to continue despite pandemic-related disruption. To prioritize patient and site staff safety several planned office visits have been converted to tele visits to allow the required data collection to meet the study objectives.

This statistical analysis plan (SAP) defines the statistical methods and data presentations to be used in the analysis and presentation of data for Aeon Biopharma, Inc protocol number ABP19002 entitled 'An Open-Label, Multicenter Study to Evaluate the Safety and Efficacy of Repeat Intramuscular ABP-450 (prabotulinumtoxinA) Injection for the Treatment of Cervical Dystonia'. This SAP has been written in accordance with ICH E9

standard operating procedures (SOPs) and using the final study protocol version 2.1 dated 13 May 2021 and electronic case report form (eCRF) version 2.0 (28 Jun 2021).

2. Objectives

2.1.1. Primary objective

• To evaluate the safety of repeat intramuscular injections of ABP-450 (150-350 units per dose) in the treatment of cervical dystonia.

2.1.2. Secondary objective

• To evaluate the efficacy of repeat intramuscular injections of ABP-450 (150-350 units per dose) in the treatment of cervical dystonia.

3. Investigational Plan

3.1. Overall Study Design and Plan

Since cervical dystonia is a chronic disease, patients typically receive medications regularly (i.e., repeated therapy), including botulinum toxin injections. For this reason, it is useful to evaluate the safety and efficacy of repeat injections of ABP-450 for the ongoing (long-term) treatment of cervical dystonia.

This is an open-label, Phase 2/3, multicenter, 52-week study of ABP-450 purified neurotoxin complex for the treatment of cervical dystonia. The study population will consist of all patients who had their initial dose of study drug in the ABP-19000 study, irrespective of treatment allocation, and who consented to being treated for cervical dystonia with ABP-450 in the ABP-19002 OLE study

At the investigator's discretion and with the patient's consent, patients will enter the OLE study at Week 8 (Week 8 will be Day 1 "rollover" for the OLE study) with the opportunity to either maintain the original Phase 2 dose or modify the dose. If there is no efficacy (or loss of efficacy) between 6 and 20 weeks in the ABP-19000 study, then patients can roll over to the OLE study at a dose determined per the investigator's discretion.

During this OLE study, patients will

receive any dose between 150 and 350 units of ABP-450, based on the investigator's discretion. There will be no additional retreatments after Week 48.

3.2. Study Estimands

[figure not shown]
For all estimands, the target population is patients diagnosed with cervical dystonia. Patients are expected to:

- Have not had previous treatment with BOTOX[®] within the last 8 weeks.
- Have not had previous treatment with ABP-450 within the last 8 weeks.
- Be receiving stable doses of treatment for focal dystonia treatment (e.g., anticholinergics and benzodiazepines)
- Meet other inclusion/exclusion criteria.

3.2.1. Primary Estimand

[figure not shown]
3.2.2. Secondary Estimands

These are the hypothetical estimands regarding alternative prohibited medications (e.g., BOTOX[®]), assuming (treatment policy) no change in background treatment and administration of treatment within the 150- to 350-unit dose range:

3.3. Treatments

Investigational study drug is a *Clostridium botulinum* toxin type A. Each vial contains 100 units of lyophilized ABP-450. All study patients, will be administered between 150 and 350 units of ABP-450, based on the investigator's discretion and clinical judgment.

There will be no additional retreatments after Week 48.

3.4. Dose Adjustment/Modifications

Patients were enrolled in the ABP-19002 OLE study with the opportunity to either maintain the original Phase 2 dose or modify the dose at the investigator's discretion. As the blind will not be broken, the placebo patients (who were entered into one of the dose groups in the ABP-19000

study) can be administered any dose between 150 and 350 units of ABP-450, based on the investigator's discretion and clinical judgment. Retreatments are also based on investigator's discretion and clinical judgment.

4. General Statistical Considerations

4.1. General considerations

The statistical principles applied in the design and planned analyses of this study are consistent with International Council for Harmonisation (ICH) E9 guidelines (ICH 1998). All descriptive summaries will be presented by dose group, treatment cycle and nominal visit/timepoint (where applicable).

All efficacy analyses will be based upon the modified Full Analysis Set (mFAS, Section 4.5.2), and all safety as well as demographic and baseline characteristic analyses will be based upon the Safety Analysis Set (Section 4.5.3). Summary of safety and efficacy analyses will be displayed by treatment group and treatment cycle. Additional analyses will be performed on selected populations as specified in the sections below.

Unless otherwise stated, the following methods will apply:

• Treatment groups: For a given assessment or event, treatment group will be assigned to a patient based on the last dose received as follows:

Range	of total dose	treatment group
a.	Non-missing dose ≤ 200 units	ABP-450 150 units
b.	> 200 to ≤ 300 units	ABP-450 250 units
c.	> 300 units	ABP-450 350 units

In addition, three dose groups (low, medium, high) based on total dose across the whole study will be assigned to a patient for a given assessment or event as follows:

Rang	e of overall total dose	Overall treatment group
a.	Non-missing dose ≤ 800 units	ABP-450 low
b.	$> 800 \text{ to} \le 1200 \text{ units}$	ABP-450 medium
c.	> 1200 units	ABP-450 high

- Continuous variables: will be summarized using summary statistics (i.e., non-missing values (n), mean, standard deviation, median, minimum, and maximum). For the summary statistics of all continuous data, minimum and maximum values will be displayed to the same level of precision as reported, unless otherwise specified. Mean and median will be displayed to one level of precision greater than the data collected. Standard deviation will be displayed to two levels of precision greater than the data collected.
- Categorical variables: will be described using the patient count and percentage in each category. When counts are presented, in cases where the count is zero, the percentage will

not be displayed to draw attention to the non-zero counts. A row denoted 'Missing' will be included in count tabulations where specified on the shells to account for missing values. The denominator for all percentages will be the number of populated patients in that treatment within the analysis set of interest, unless otherwise specified. Frequency statistics will be displayed using one decimal place except for the display of 100% frequency which will be displayed as 'XX (100)'.

- Rules for multiple assessments: To summarize data collected over time, summary tables will be presented by scheduled visit. Unscheduled visits may be included in specific summaries (such as worst post-baseline measurement) and will be described in the relevant sections. Both scheduled and unscheduled visits will be included in the data listings.
- Date and time display conventions: The following display conventions will be applied in all outputs where dates and/or times are displayed:

Date only: DDMMMYYYY

Date and time: DDMMMYYYY HH:MM

Partial dates will be listed as such (i.e., where day or day and month is missing, only MMMYYYY or YYYY will be displayed, respectively).

- Multiple comparisons: There will be no statistical adjustment for multiplicity.
- Treatment terminology and order to be used in TLF outputs:
 - Unless specified, the following labels will be used for summary tables:
 - a. ABP-450 150 units
 - b. ABP-450 250 units
 - c. ABP-450 350 units
 - For summary of disposition, demography, medical history, prior medications, and first secondary estimand, the following will be used:
 - a. ABP-450 low
 - b. ABP-450 medium
 - c. ABP-450 high

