4.3. Sample Size

All eligible patients who had their initial dose of study drug in the ABP-19000 study, irrespective of treatment allocation, and consented to being treated with ABP-450 can be enrolled in this OLE (i.e., ABP-19002) study.

Approximately 59 patients could enroll in this OLE study from the ABP-19000 study. As there will be no comparative analyses, study power and sample size justifications are not required.

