5.1. Disposition

Patient disposition will be summarized by overall treatment group and presented in a listing for patients in the Enrolled Set. The disposition of patients will include the number and percentage of patients for the following categories:

- Patients enrolled.
- Patients included in the mFAS.
- Patients included in the SAF.
- Patients included in the SAFR.
- Patients who discontinued treatment with corresponding reasons for treatment discontinuation.
- Patient included in the SAF with corresponding reasons for treatment discontinuation.
- Patients who withdrew from the study with corresponding reasons for study withdrawal.

The reasons for discontinuation of ABP-450 treatment or withdrawal from the study include:

• Adverse Event

- Death
- Lack of Efficacy
- Lost to Follow-up
- Non-Compliance with Study Drug
- Physician Decision
- Pregnancy
- Study Terminated by Sponsor
- Withdrawal by Subject
- Other

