5.2. Protocol Deviations

A listing of patients with protocol deviations will be provided.

6. Demographics and Baseline Characteristics

Demographic and baseline information will be summarized descriptively by overall treatment group (low, medium, high) as described in Section 4.1 using the mFAS and SAF and presented in listings using SAF.

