7.2. Study Treatments

7.2.1. Extent of Exposure to ABP-450

The number and percentage of patients exposed to study treatment at each visit within each treatment cycle will be summarized descriptively for categorical parameters by treatment group, while the cumulative number of doses and cumulative dose at each visit within each treatment cycle and total ABP-450 administered overall will be summarized descriptively for continuous parameters as described in Section 4.1, using the SAF.

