8.1.2. Overall Summary of Adverse Events

An overall summary of TEAEs will be summarized by treatment group and treatment cycle by providing the number and percent of patients who experience the following:

An overall summary of the number and percentage of patients with at least one TEAE will be presented by SOC and PT. At each level of patient summarization, a patient is counted once if the patient reported one or more events starting in each treatment group in each treatment cycle, and across all cycles (by overall total doses of low, medium, and high). Percentages will be calculated out of the number of patients in the SAF. The table will be sorted by SOC and PT in descending order of incidence from the SOC and PT with the highest total incidence to the SOC and PT with the lowest total incidence. Summaries and listings will be presented for the SAF.

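### The overall low/medium/high groups are cut on cumulative units, so they mix dose per injection with number of injections, yet disposition and the across-cycle AE and SAE tables are shown by them

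*SAP*

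**What the plan says.** SAP 4.1 defines two groupings. The first uses the last dose received before an assessment or event, with bands up to 200, above 200 to 300, and above 300 units. The second is a separate overall grouping: "three dose groups (low, medium, high) based on total dose across the whole study will be assigned to a patient". Low is a total of 800 units or less, medium is above 800 to 1200, and high is above 1200.

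The overall grouping is used in several places:

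- SAP 4.1, output labels: "For summary of disposition, demography, medical history, prior medications, and first secondary estimand, the following will be used", followed by low, medium and high.
- SAP 5.1: "Patient disposition will be summarized by overall treatment group". This table includes the reasons for stopping treatment and for leaving the study.
- SAP 6: "Demographic and baseline information will be summarized descriptively by overall treatment" group. SAP 6.2 and 7.1 do the same for medical history and for prior and concomitant medications.
- SAP 8.1.2 and 8.1.6: TEAEs and SAEs are shown by last-dose group within each cycle, and also "across all cycles (by overall total doses of low, medium, and high").

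The number of injections is not fixed. SAP 3.4 states "Retreatments are also based on" the investigator's discretion and judgment, and SAP 3.3 allows retreatment up to Week 48 at 150 to 350 units each time. SAP 7.2.1 separately summarises "cumulative number of doses and cumulative dose at each visit within each treatment cycle and total ABP-450 administered overall". SAP 4.3 says that, since no comparisons between groups are planned, "study power and sample size justifications are not required".

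**The concern.** Total units equal mean dose per injection times number of injections. The second factor arises after entry and depends on retention and on retreatment decisions, so grouping on the product groups partly on outcome.

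For disposition this is circular. A patient who stops early accumulates few units, is placed in low for that reason, and is then counted there as a discontinuation. For the across-cycle AE and SAE tables, columns with more injections have had more opportunities for an event. A rise from low to high can therefore appear when dose per injection has no effect.

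The SAP calls these columns dose groups, so a reader will take a pattern across them as a dose pattern. Safety of repeat dosing is the primary objective, and the across-cycle tables give the overall view of it.

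**Working it through.** The plan gives no figure of its own to reproduce on this point. The check uses the cut-offs in SAP 4.1 (800 and 1200 cumulative units; 200 and 300 units per injection) and the permitted 150 to 350 units per injection in SAP 3.3. Below, *n* is the number of injections counted in the total.

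**1. Relation between the two groupings.** 800 / 200 = 4 and 1200 / 300 = 4. The cumulative cuts are the per-injection cuts times four.

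**2. What the cuts mean for each n.** The cut-offs on mean dose are 800/n and 1200/n. The last column is the share of the 200-unit-wide permitted range in which the overall group differs from the 200/300 band.

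| n | Possible total | Cuts on mean dose | Share that differs |
|---|---|---|---|
| 1 | 150–350 | all low | 150/200 = 75% |
| 2 | 300–700 | all low | 150/200 = 75% |
| 3 | 450–1050 | 266.7 / 400 | (66.7 + 50)/200 = 58.3% |
| 4 | 600–1400 | 200 / 300 | 0% |
| 5 | 750–1750 | 160 / 240 | (40 + 60)/200 = 50% |
| 6 | 900–2100 | 133.3 / 200 | (50 + 100)/200 = 75% |

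The shift is always downward at one to three injections and always upward at five or six. A constant 250 units is low at three injections (750), medium at four (1000) and high at five (1250). Two injections of 350 units (700, low) rank below six of 150 units (900, medium). These are shares of a dose range. The share of patients affected cannot be computed from the visible text.

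**3. Effect on disposition (illustration; all inputs assumed).** Patients are in equal thirds at constant 150, 250 and 350 units, with 10% dropout after each injection, the same at every dose. With a maximum of four injections, the probabilities of n = 1, 2, 3, 4 are 0.1, 0.09, 0.081 and 0.729. True discontinuation is 1 − 0.729 = 27.1% at every dose. Expressing each dose third as 1:

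- Low holds all of 150 units, n = 1–3 at 250, and n = 1–2 at 350: 1 + 0.271 + 0.190 = 1.461. Discontinued: 0.271 + 0.271 + 0.190 = 0.732. Displayed: 0.732/1.461 = 50.1%.
- Medium holds n = 4 at 250 and n = 3 at 350: 0.729 + 0.081 = 0.810. Discontinued: 0.081. Displayed: 10.0%.
- High holds only n = 4 at 350: 0.729. Discontinued: none. Displayed: 0%.

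The same enumeration for other maxima gives:

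| Maximum injections | True, every dose | Low | Medium | High |
|---|---|---|---|---|
| 4 | 27.1% | 50.1% | 10.0% | 0% |
| 5 | 34.4% | 55.1% | 100% | 5.3% |
| 6 | 41.0% | 100% | 20.7% | 14.7% |

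Over dropout of 5 to 15% and a maximum of four to six, low ranges from 30.9% to 100% and high from 0% to 21.9%. No minimum retreatment interval is visible. With the last retreatment at Week 48, assumed intervals of 8, 12 or 16 weeks would allow 7, 5 or 4 injections (48/interval + 1).

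**4. Effect on across-cycle AE incidence (illustration).** Take the maximum-four case and assume a 10% AE risk per cycle at every dose. P(at least one AE given n) = 1 − 0.9^n, which is 0.1, 0.19, 0.271 and 0.3439 for n = 1 to 4.

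- True, every dose: 0.1×0.1 + 0.09×0.19 + 0.081×0.271 + 0.729×0.3439 = 0.2998, or 30.0%.
- Low: (0.2998 + 0.0491 + 0.0271)/1.461 = 25.7%.
- Medium: (0.2507 + 0.0220)/0.810 = 33.7%.
- High: 34.4%.

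At a constant 250 units and the same assumed risk, incidence is 27.1% at three injections (low), 34.4% at four (medium) and 41.0% at five (high). The gradient comes from the number of injections alone.

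**The case against.** The strongest reply is that cumulative exposure is a legitimate axis in a repeat-dosing safety study. The SAP defines it openly alongside the last-dose grouping and never says that the two should agree. On that view the differing shares describe two variables and show no error. Cumulative exposure is indeed legitimate as an exposure summary. It does not work as the column variable for outcomes, such as stopping treatment, that help determine it.

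Other points carry some weight:

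- The by-cycle AE and SAE tables use last dose and are unaffected. They do not repair disposition or the across-cycle columns.
- The outputs concerned are described as non-comparative, and dose is chosen by the investigator, so patterns between columns are confounded under any grouping. This limits the severity.
- The AE distortion is small in patient numbers. With about 59 patients (SAP 4.3), high in the maximum-four illustration holds 59/3 × 0.729, about 14 patients, so the 8.7-point gap from low is about one patient.
- The SAP does not say whether ABP-19000 units count or whether the total is final or to date. The bounds above hold for whichever injections are counted, provided each is within 150 to 350 units. A to-date total gives the same group at the time of discontinuation.
- The 100% figures depend on assumed maxima of five and six. The mixing itself does not, because fewer than four injections are always possible.

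**Conclusion.** The concern holds and should be fixed. The rule in SAP 4.1 makes the overall group depend on the number of injections. It agrees with the SAP's own per-injection bands across the whole permitted range only at exactly four injections; at other counts from one to six, 50% to 75% of that range changes group. Disposition is the most exposed output. The across-cycle TEAE and SAE tables are affected more modestly, in a direction that can look like a dose response.

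The bounds and shares follow from the SAP's cut-offs. The discontinuation and AE percentages rest on assumed dropout, dose mix and maximum number of injections, and only illustrate the mechanism. No effect on the primary estimand is shown. The model for the first secondary estimand is not visible, so nothing is claimed beyond its display by these groups, and the direction of any bias in efficacy is unknown.

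**What to change.** Replace the cumulative cut-offs in SAP 4.1.

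- For disposition, demography, medical history, prior medications and the first secondary estimand, define the overall group by the first OLE dose, using the existing bands (up to 200, above 200 to 300, above 300 units). It is fixed at entry. Align the concomitant medication summary in SAP 7.1.
- For the across-cycle TEAE and SAE tables, use the same group, or mean units per OLE injection (total units divided by number of injections) with the same bands. State which, and show the number of injections per column.
- Keep cumulative dose in SAP 7.2.1, where it is already planned as an exposure summary.
- State how enrolled but undosed patients appear in disposition, since they have no dose group under either rule.

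The cost is one derived variable and revised wording, with no new data. First dose ignores later dose changes. Mean dose reflects them but is itself known only after entry. Dose remains the investigator's choice, so the displays stay descriptive.
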